#### 6.1.4.2 Long-term Follow-up / Trial Termination

All SAEs ongoing at the 28-Day Safety Follow-up visit must be monitored and followed up by the Investigator until stabilization or until the outcome is known, unless the subject is documented as "lost to follow-up." In addition, all trial drug-related SAEs occurring after 28-Day Safety Follow-up visit and ongoing at the Safety Follow-up visit have to be followed up in the same manner.

Subjects without PD at the 28-Day Safety Follow-up visit will be followed up for disease progression (CT / MRI scans every 12 weeks) until PD.

After the 28-Day Safety Follow-up visit, subjects will be followed quarterly ( $\pm$  14 days) for survival (including assessment of any further anticancer therapy). The survival follow-up will continue until 1 year after the last subject receives the last dose of M7824.

### 6.1.5 Blood Consumption for Clinical Assessments

The overall amount of blood to be drawn from a single subject must not exceed 120 mL/day and 550 mL in an 8-week period for safety laboratory testing, pregnancy testing, exploratory biomarker investigation, and antibody evaluation.

### 6.2 Demographic and Other Baseline Characteristics

The assessments and procedures described in this section must be performed during the Screening period.

#### 6.2.1 Demographic Data

The following demographic data will be recorded:

- Subject identifier
- Date of birth
- Sex

- Ethnicity
- Race

#### 6.2.2 Diagnosis of Tumor

The tumor disease information that will be documented and verified at the Screening visit for each subject includes:

- Detailed history of the tumor, including histopathological diagnosis, grading and staging in accordance with the American Joint Cancer Committee (7th Edition) Tumor Node Metastasis Classification at diagnosis (AJCC TNM).
  - $\circ~$  The M category (M0 or M1) of the tumor at the time of study entry, based on screening assessments.
- All therapy used for prior treatment of the tumor (including surgery, radiotherapy and chemotherapy, immunotherapy, etc.).
- Any other conditions that were treated with chemotherapy, radiation therapy, or immunotherapy.
- Current cancer signs and symptoms and side effects from current and / or previous anticancer treatments.
- Current cancer disease status.

### 6.2.3 Medical History

In order to determine the subject's eligibility to the trial, a complete medical history of each subject will be collected and documented during Screening, which will include, but may not be limited to, the following:

- Past and concomitant non-malignant diseases and treatments.
- All medications taken and procedures carried out within 30 days prior to Screening.

For the trial entry, all the subjects must fulfill all inclusion criteria described in Section 4.3.1, and none of the subjects should have any exclusion criterion from the list described in Section 4.3.2.

### 6.2.4 Vital Signs and Physical Examination

Vital signs including body temperature, respiratory rate, heart rate (after 5-minute rest), and arterial blood pressure (after 5-minute rest), body weight and height will be recorded at study entry.

Physical examinations will be performed according to **Tables 1-3**. An ophthalmology examination including slit lamp evaluation inclusive of the anterior segment and with visual acuity should be conducted.

The ECOG PS will be documented during the Screening phase.

## 6.2.5 CT or MRI Scans for Tumor Assessment at Baseline

A CT scan or MRI (if MRI is used, CT of chest is mandatory) of the chest, abdomen, and pelvis will be performed within 28 days prior to trial treatment start in order to document the baseline status of the tumor disease using iRECIST 1.1 target and non-target lesions. However, if the results of a CT scan or MRI performed within 4 weeks prior to first treatment are available, the Screening CT / MRI does not need to be performed.

A bone scan should be done at Screening as clinically indicated.

### 6.2.6 Cardiac Assessments

A 12-lead EKG will be recorded at Screening. The EKG will be recorded after the subject has been in a supine position breathing quietly for 5 minutes. The EKG results will be used to evaluate the heart rate, atrial-ventricular conduction, QR, QT, and corrected QT intervals, and possible arrhythmias.

The EKGs will be documented by recording date and time of collection. All EKG results must be reviewed at the site by the Investigator or a medically qualified designee for clinical management of the subject. EKGs are to be performed according to local procedures and will NOT be digitally uploaded.

The Investigator will judge the overall interpretation as normal or abnormal. If abnormal, it will be decided if the abnormality is clinically significant or not clinically significant and the reason for the abnormality will be recorded on the eCRF (Prometheus). Abnormal values will not be recorded as AEs unless they are the reason for discontinuation of the trial IMP due to AEs or are SAEs.

## 6.2.7 Clinical Laboratory Tests

Blood samples will be collected at screening for clinical laboratory parameter evaluations. These clinical laboratory test results will serve not only as the baseline values for subsequent safety clinical laboratory evaluations during the trial, but also help to make sure that each enrolled subject fulfills all the trial entry criteria as listed in Section 4.3.1 and does not meet any of the trial exclusion criteria for laboratory parameters as listed in Section 4.3.2. Detailed description of laboratory assessments is provided in Section 4.4.3.

### 6.2.8 ctDNA testing

Guardant360 is a next-generation sequencing (NGS) panel of 70 clinically actionable onco- and tumor suppressor genes utilizing digital sequencing of cell-free circulating tumor DNA (cfDNA) isolated from a simple, non-invasive blood draw. It is medically indicated for the prevention of a repeat invasive biopsy in advanced cancer patients when the initial biopsy is insufficient (QNS) or unavailable/unobtainable as well as when cancer has progressed or recurred despite treatment. The test detects single nucleotide variants via complete exon sequencing in 70 genes, copy number

amplifications in 16 genes, small indels in EGFR, ERBB2 and MET exon 14 skipping, and fusions in ALK, FGFR2, FGFR3, RET, ROS1 and NTRK1. The genes are selected because mutations in these genes have FDA-approved matched therapies or are eligible for late phase clinical trials, as well as non-druggable genes with high prevalence alterations that may be helpful in monitoring for molecular response/non-response such as TP53.

Guardant360 is an advanced diagnostic laboratory test (ADLT) offered by a sole source laboratory certified by the Clinical Laboratory Improvement Amendments (CLIA) for high complexity (molecular pathology) testing and accredited by the College of American Pathology (CAP). Due to high rates of false positives with traditional NGS assays when tumor DNA is in low concentrations, the majority of "liquid biopsy" methods interrogating cell-free DNA have been limited to hotspot analyses. In contrast, the ultra-high specificity (> 99.9999%) of the digital sequencing method enables the sequencing of long, targeted regions (146,000 base pairs) without false positives. Complete exons are sequenced for all exons in 30 genes and the critical exons (those reported as having a somatic mutation in COSMIC) in 40 additional genes. Thus, its key differentiating characteristic from other "liquid biopsy" methods is the ability to sequence complete exons in many genes, in contrast to gene hotspot testing.

Advantages of the Guardant360 cell-free DNA NGS methodology versus solid tumor tissue-based NGS are:

- 1. An invasive needle or surgical biopsy is avoided with ctDNA, reducing costs and complications.
- 2. CtDNA provides a quantitative measure (concentration or mutant allele frequency) of mutations present whereas solid tumor biopsy typically provides a qualitative result (mutation either present or not detected). The quantitative cfDNA result may be followed over time to monitor response to treatment and evolution of acquired resistance.
- 3. CtDNA sequencing identifies both germline and somatic mutations in the same sample.
- 4. The assay failure rate is for ctDNA is less than 0.5% (in the first 9,000+ samples) compared to 15%-25% failure rates of tissue-based NGS related to insufficient quantity of tissue (QNS).

Guardant360 utilizes algorithmic methods to encode and ultimately decode inputs and outputs from massively parallel deep sequencing analysis. By leveraging signal transduction processing technology where voice or image data is digitally encoded before transmission and then decoded post-transmission, this NGS method, known as Digital SequencingTM, enables signal interference to be reduced by two orders of magnitude or more . Four validation studies have been published with concordance to tissue biopsy-based genomic testing . With high enough sensitivity and specificity to robustly quantitate ctDNA from blood, this approach has the potential to evaluate the multiple genomic targets required in NCCN guidelines, to act as a "summary" of the different tumor clones in patients with intra-tumor and inter-tumor heterogeneity, and to prevent the time

delays, costs and complications inherent in invasive biopsies. The analytical and clinical validation of Guardant360 is conducted in conformance with evidentiary standards established by the Standards for Reporting of Diagnostic Accuracy (STARD), REporting of tumor MARKer Studies (REMARK), Evaluation of Genomic Applications in Practice and Prevention (EGAPP), and the recent Next-generation Sequencing: Standardization of Clinical Testing (Nex-StoCT) biomarker guidelines .

#### Methodology

The gene panel was selected to focus on those genomic alterations that are currently actionable defined as being targets of sensitivity or resistance to an FDA-approved matched therapy and/or a targeted therapy in clinical trials. The test simultaneously sequences the 70 cancer-related genes to an average depth of coverage of greater than 8,000X. To summarize, cell-free DNA is extracted from plasma and genomic alterations are analyzed by massively parallel paired end synthesis-by-sequencing of amplified target genes utilizing an Illumina Next-Seq platform complemented by systematic end-to-end process optimization including conversion of cell-free DNA fragments into digital sequences, improvements in the Illumina next generation sequencing process itself, followed by bioinformatics algorithms which enable ctDNA to be measured as a quantitative percentage of total cell-free DNA.

Two 10mls of whole blood are collected in Streck Cell-Free DNA Blood Collection (Streck) tubes, which contain a proprietary formaldehyde-free preservative in that stabilizes white blood cells, preventing the release of genomic DNA and allowing shipping and stability for seven days without need for refrigeration, cold bricks or preliminary centrifugation prior to shipping.

After digital libraries are produced, the sample is sequenced and post-sequencing data is processed using bioinformatics algorithms to quantify the absolute number of unique DNA fragments at a given nucleotide position. This proprietary process is referred to as Digital SequencingTM and enables reporting of the fractional concentration (mutant allele frequency) of a given SNV. Circulating cell-free DNA is mostly derived from leukocyte lysis (germline) and generally a much smaller amount of tumor DNA is derived from cancer cell apoptosis/necrosis. All of the cell-free DNA fragments, including leukocyte-derived and tumor-derived, are simultaneously sequenced with up to single molecule sensitivity. In other words, both tumor DNA and "normal"/germline DNA are sequenced and measured in the same sequencing assay. The fractional concentration or mutant allele frequency for a given mutation is calculated as the fraction of circulating tumor DNA harboring that mutation in a background of wild-type cell-free DNA fragments. The analytic sensitivity reaches detection of 1-2 single mutant cell-free DNA molecules from a 10 ml blood sample.

#### Gene list and genomic alterations in the Guardant360 Panel

## Guardant360 Panel 2015 All NCCN Somatic Genomic Targets in a Single Test

## 6.3

#### **Efficacy Assessments**

For all subjects, tumor response assessment will be performed by CT scan or MRI (if MRI is used, CT of chest is mandatory. All the scans performed at baseline and other imaging performed as clinically required (other supportive imaging) need to be repeated at subsequent visits. In general, lesions detected at baseline need to be followed using the same imaging methodology and preferably the same imaging equipment at subsequent tumor evaluation visits.

Skin metastasis can be used as target lesions according to iRECIST 1.1 using measurements by caliper, if they fulfill iRECIST 1.1 for target lesions as described below. The presence of new cutaneous lesions will be considered diagnostic of progression for iRECIST 1.1, even if not imaged. For each subject, the Investigator will designate 1 or more of the following measures of tumor status to follow for determining response: CT or MRI images of primary and / or metastatic tumor masses, physical examination findings, and the results of other assessments. All available images collected during the trial period will be considered. The most appropriate measures to evaluate the tumor status of a subject should be used. The measure(s) to be chosen for sequential evaluation during the trial have to correspond to the measures used to document the progressive tumor status that qualifies the subject for enrollment. The tumor response assessment will be assessed and listed according to the Schedule of Assessments (refer to **Tables 1-3**).

The foreseen treatment duration is until documentation of PD, unacceptable toxicity, or any criterion for withdrawal from the trial or IMP occurs (see Section 4.5).

GUARDANTHEALTH

The treatment should be stopped immediately, if the subject does not tolerate M7824 anymore or if therapeutic failure occurs, which requires urgent treatment with an additional drug or results in clinically significant progression / deterioration.

Tumor responses to treatment will be assigned based on the evaluation of the response of target, non-target, and new lesions according to iRECIST 1.1 (all measurements should be recorded in metric notation).

• To assess objective response, the tumor burden at baseline will be estimated and used for comparison with subsequent measurements. At baseline, tumor lesions will be categorized in target and non-target lesions according to iRECIST 1.1

Results for these evaluations will be recorded with as much specificity as possible so that pre- and post-treatment results will provide the best opportunity for evaluating tumor response.

Any CR or PR should be confirmed according to iRECIST 1.1.

The Investigator may perform scans in addition to a scheduled trial scan for medical reasons or if the Investigator suspects PD.

As outlined in Section 4.1, treatment should continue with M7824 if the patient has PD provided:

- There are no new Grade 2 or greater symptoms or significant worsening of existing symptoms.
- There is no decrease in ECOG PS.
- In the opinion of the Investigator, the subject does not require new anticancer therapy.

PD and any of the above conditions not satisfied results in study discontinuation.

Subjects who have experienced a confirmed PR or CR should continue treatment through the end of 12 months, although additional treatment is possible. If the Investigator believes that a subject may benefit from treatment beyond 12 months, it may be permissible after discussion with the principal investigator.

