## **3** Trial Objectives

### 3.1 Primary Objective

The primary objectives of this study are to estimate efficacy of M7824 with:

• Objective response rate (ORR) in microsatellite instability-high (MSI-H) patients who have progressed on immune checkpoint blockade therapy (Cohort A-C).

OR

ORR in patients with treatment-refractory, consensus molecular subtype 4 (CMS4) mCRC patients coadmnistered SBRT (Cohort B). While SBRT is preferred, IMRT or 3D conformal techniques may be utilized at the discretion of the treating radiation oncologist depending on the dose to surrounding normal tissues. Patient will receive a total dose of 24Gy over three days with one of the following modalities, at the discretion of the treating radiation on cologist: SBRT, IMRT and 3D conformal.

OR

• Clearance of ctDNA in ctDNA(+) patients with resected mCRC following completion of standard-of-care therapy (Cohort D).

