### 4.1.1.2 Cohort B – CMS4 mCRC

This is a phase 2, single arm, Simon's optimal two-stage design to assess ORR in treatmentrefractory CMS4 mCRC receiving M7824 with SBRT. The hypothesis is that efficacy of M7824 coadministered with SBRT will be demonstrated in patients with CMS4 mCRC

Patients successfully enrolled will have had CMS4 classification after characterization of their pretreatment primary tissue biopsy. M7824 will be administered intravenously at a dose of 1200mg every 14 days (+/- 7 days). The first dose of M7824 will be administered alone. After the second dose of M7824, patients will receive SBRT for a total dose of 24Gy over three days, with first treatment of radiotherapy administered within 7 days of completion of the second dose of M7824 (cycle 1, day 15). Radiotherapy must be completed prior to the third dose of M7824. While SBRT is preferred, IMRT or 3D conformal techniques may be utilized at the discretion of the treating radiation oncologist depending on the dose to surrounding normal tissues. Patient will receive a total dose of 24Gy over three days with one of the following modalities, at the discretion of the treating radiation oncologist: SBRT, IMRT and 3D conformal.

M7824 will be continued until documented PD or unacceptable toxicity. Tumor assessments will be performed every 8 weeks. Progressive disease, stable disease, partial response, and complete response will be defined by iRECIST 1.1. Patients who discontinue due to toxicity will continue to be assessed via imaging until documented PD.

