### 4.1.5.2 Cohort B

The first data cut-off for the interim analysis will be 12 weeks after the  $15^{\text{th}}$  subject enrolled has received study treatment. A decision to continue on to the target 29 patients will be based on the number of responses observed. If 2 or more confirmed responses are observed, the primary data cut-off for the analysis will be 24 weeks after the last subject (n=29) received study treatment.

The final data cut-off will be 1 year after the last subject has received the last dose of M7824.

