## 4.2.1.2 Cohort B

This is a phase II, single arm, Simon two-stage design to assess efficacy of M7824 as an abscopal phenomenon with radiation to a single metastatic lesion in patients with treatment-refractory, CMS4 mCRC receiving M7824. Tumors  $\geq$  7.0 cm in largest diameter should be excluded from receiving radiation as part of this study. As previously described, TGF $\beta$  represents an immune resistance mechanism via recruitment of immunosuppressive cells and downregulation of existing anti-tumoral responses within the TME. TGF- $\beta$  signaling may also promote resistance to an abscopal phenomenon in patients with mCRC administered immunotherapy with radiation. The trial design is also justified based on pre-clinical evidence that CMS4 mCRC demonstrate an intrinsically inflamed, immunosuppressive phenotype mediated by upregulation of TGF- $\beta$  signaling.

Restriction in this study to CMS4 comes from a number of preclinical studies implicating it with upregulation of TGF- $\beta$  activation. Several of the hallmark features including EMT, stromal infiltration, angiogenesis and matrix remodeling are explained by some of the pleotropic effects of TGF- $\beta$ . TGF $\beta$  represents an immune resistance mechanism via recruitment of immunosuppressive cells and downregulation of existing anti-tumoral responses within the TME. CMS4 is associated with poorer cancer specific outcomes and non-benefit to current adjuvant chemotherapy strategies, and therefore novel effective therapies ae needed for this subpopulation of mCRC.

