## 4.3 Selection of Trial Population

### 4.3.1 Inclusion criteria

- 1. Histologically or cytologically confirmed adenocarcinoma of the colon or the rectum that is metastatic or unresectable (cohort B); or histologically or cytologically confirmed adenocarcinoma of the colon or the rectum following resection of the primary tumor and metastatic disease, following completion of standard-of-care perioperative therapy at the discretion of the treating provider (cohort D).
- 2. Confirmation of:
  - a. Cohort A-C: microsatellite instability
  - b. Cohort B: CMS4 CRC classification on pretreatment primary tumor.
  - c. Cohort D: microsatellite stability
- 3. Age >18 years at time of study entry.
- 4. Ability to provide written informed consent.
- 5. Documented progression to prior therapies (Cohorts A-C and B):
  - a. Cohort A-C: Disease progression following prior immune checkpoint blockade therapy
  - b. Cohort B: Progression or intolerance to at least 2 prior lines of standard therapy for unresectable or metastatic CRC
- 6. Available primary tumor tissue for CMS4 biomarker assessment (cohort B)
- 7. Life expectancy  $\geq 12$  weeks as judged by the treating physician.
- 8. Eastern Cooperative Oncology Group (ECOG) performance status of 0 or 1.
- 9. Measurable disease according to iRECIST v1.1 (Cohorts A-C and B). For cohort B, measureable lesions must be identified apart from the irradiated tumor lesion. Patients in cohort D must have no evidence of radiographically evident disease at the time of study entry.
- 10. Adequate hematological function, defined by ANC  $\geq 1.0 \times 10^{9}$ /L, lymphocyte count  $\geq 0.5 \times 10^{9}$ /L, platelet count  $\geq 100 \times 10^{9}$ /L, and Hgb  $\geq 9$  g/dL (in absence of blood transfusion).
- Adequate hepatic function defined by a total bilirubin level ≤ 1.5 × the upper limit of normal (ULN), an AST level ≤ 2.5 × ULN, and an ALT level ≤ 2.5 × ULN. If liver metastases are present, then it is acceptable for AST level ≤ 5.0 × ULN, and an ALT level ≤ 5.0 × ULN.
- 12. International normalized ratio (INR) < 1.5
- 13. Adequate renal function defined by an estimated creatinine clearance >30 mL/min according to the Cockcroft-Gault formula or be measure for creatinine clearance from 24 hour urine collection.

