# 7.1.2 The total sample size of this cohort is 15 patients. With this sample size, the half-width of the 95% confidence interval for the estimated response rate will be at most 0.253. Cohort B

For this cohort, the Simon's Optimum two-stage design will be implemented. A historical response rate of 5% and a target response rate of 25% are assumed under the null and the alternative hypotheses, respectively. In the first stage, we will enroll 15 patients; if 1 or fewer achieves a best response of CR/PR, we will stop enrolling patients. Otherwise, we will continue to enroll all 29 patients and the treatment is deemed as promising if there are 4 or more responders out of these 29 patients. The design has a type I error rate of 0.042, a 90% power and a probability of early termination of 82.9% under the null hypothesis. Patient enrollment will be temporarily suspended when the enrollment for the first stage patients has been completed yet not enough responders have been observed to trigger the start of second stage.

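### Cohort B is framed as a test of an abscopal effect, but the response rules do not expressly keep the irradiated lesion out of the target lesions or out of the primary ORR

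*Combined protocol and SAP*

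**What the plan says.** **Aim.** Section 4.2.1.2 says Cohort B is designed "to assess efficacy of M7824 as an abscopal phenomenon with radiation to a single metastatic lesion". Section 3.1 sets the primary objective as ORR in patients who also receive SBRT. Section 4.1.1.2 states: "The hypothesis is that efficacy of M7824 coadministered with SBRT will be demonstrated in patients with CMS4 mCRC".

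**Eligibility.** Inclusion criterion 9 (Section 4.3.1): "For cohort B, measureable lesions must be identified apart from the irradiated tumor lesion".

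**Response rules.** Section 6.3: "At baseline, tumor lesions will be categorized in target and non-target lesions according to iRECIST 1.1", and "Tumor responses to treatment will be assigned based on the evaluation of the response of target, non-target, and new lesions according to iRECIST 1.1". Section 7.3.1 defines the primary endpoint as CR plus PR in the same words for Cohorts A-C and B. Section 7.5.2.1.1 determines response by iRECIST 1.1 with no restriction on lesions. None of these mentions the irradiated lesion.

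**Decisions.** Section 7.1.2 stops Cohort B at 1 or fewer responders in 15. Otherwise enrolment goes to 29, and "the treatment is deemed as promising if there are 4 or more responders out of these 29 patients". The null is a historical rate of 5% and the target is 25%. For stage 1, Section 4.1.5.2 says "If 2 or more confirmed responses are observed", while Section 7.1.2 speaks of best response.

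**The concern.** An abscopal effect is a response outside the radiation field. Criterion 9 ensures that every Cohort B patient enters with disease in which such a response can be measured. An entry criterion does not, however, define which lesions enter the baseline sum or the CR/PR call, and the sections that do define this are silent on the irradiated lesion.

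If that lesion is chosen as a target, its shrinkage after 24 Gy lowers the sum of diameters whether or not M7824 has any effect elsewhere. Two assessors could follow Section 6.3 correctly and score the same patient differently. The counts drive two decisions, opening stage 2 and calling the treatment promising, and either can turn on a single patient. A positive result could then not be read with confidence as activity outside the field.

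**Working it through.** **1. Timing.**
- Baseline scan: within 28 days before treatment (Section 6.2.5).
- Radiation: after dose 2 and before dose 3 (Section 5.2.2; Table 2, footnote w).
- First response scan: week 8, then every 8 weeks (Section 6.1.2).

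In-field shrinkage therefore falls between baseline and the first response scan. If it lasts, it is also present at the next scan, so requiring confirmation does not remove it.

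**2. The plan's own figures.** Inputs from Section 7.1.2: n1 = 15, stop at 1 or fewer; n = 29 (14 more patients), promising at 4 or more; rates 0.05 and 0.25. With X1 and X2 the responders in the two stages:

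P(promising) = P(X1=2)·P(X2≥2) + P(X1=3)·P(X2≥1) + P(X1≥4)

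- At 0.05: 0.1348×0.1530 + 0.0307×0.5123 + 0.0055 = 0.0418 (plan: 0.042).
- At 0.25: 0.900 (plan: 90%).
- Early termination at 0.05: P(X1≤1) = 0.4633 + 0.3658 = 0.829 (plan: 82.9%).

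All three reproduce. The gap is in the endpoint definition, not in the sample-size arithmetic.

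**3. One-patient margins at 5%.**
- P(X1=1) = 0.366; one further responder would open stage 2.
- P(stage 2 opens and the total is 3) = P(X1=2)·P(X2=1) + P(X1=3)·P(X2=0) = 0.1348×0.3593 + 0.0307×0.4877 = 0.063; one further responder would change the conclusion.

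These margins belong to the design and apply to any misclassified patient, whatever the cause.

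**4. Illustration only.** Assume an out-of-field ORR of 5%, plus d percentage points of patients who respond only through the irradiated lesion. The documents give no value for d.

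| d | Rate used | P(stage 2 opens) | P(promising) |
|---|---|---|---|
| 0 | 0.05 | 0.171 | 0.042 |
| 1 | 0.06 | 0.226 | 0.072 |
| 2 | 0.07 | 0.283 | 0.111 |
| 3 | 0.08 | 0.340 | 0.157 |

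Three points is 29 × 0.03 = 0.87 patients.

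**5. When could the irradiated lesion alone produce a PR?** Assume PR needs a 30% fall in the sum (the documents do not state the threshold). Let f be the lesion's share of the baseline sum and g the fractional shrinkage of the other targets.

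In-field shrinkage needed = (0.30 − (1 − f)·g) / f; minimum share = (0.30 − g) / (1 − g)

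- g = 0: minimum share 30%. Shares of 30%, 40%, 50% and 60% need 100%, 75%, 60% and 50%.
- g = −0.10 (growth elsewhere): minimum share 36%; a 40% share needs 90%.
- g = 0.15: minimum share 18%; a 40% share needs 52.5%.

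There must also be no progression or new lesion elsewhere. The size limit of under 7.0 cm for irradiated tumors (Section 4.2.1.2) does not rule out large shares: an assumed 60 mm lesion makes up 30% or more of the sum when the other targets total 60/0.30 − 60 = 140 mm or less.

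**The case against.** **The intent is already visible.** Criterion 9, read with the abscopal aim, points to measurement outside the field, and Section 6.3 asks for the most appropriate measures of tumor status, which lets an investigator leave the irradiated lesion out. This stands as evidence of intent. It leaves the choice to the assessor. Section 6.3 also ties the chosen measures to those that documented the qualifying progression, which could include that lesion.

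**A reader might infer that the protocol allows the irradiated lesion as a target.** That goes too far. Lesion selection is delegated to iRECIST 1.1, which is not reproduced. The documents support only that the lesion is not expressly excluded.

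**A reader might infer that an in-field response is a false response.** That holds only on the abscopal reading. Sections 3.1, 4.1.1.2 and 7.5.2.1.1 can be read as ORR of M7824 with radiation, where in-field response legitimately counts. The documents do not settle which is meant. On the combination reading, the 5% null should also include in-field response, and Section 7.1.2 does not say whether it does.

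**Confirmation at stage 1.** Only Section 4.1.5.2 ties that count to confirmed responses. Section 4.1.2.2 refers to radiographic response and Section 7.1.2 to best response, while Section 7.5.2.1.1 excludes unconfirmed responses from the final analysis. So it is not settled that the stage 1 count needs confirmation.

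**Conclusion.** The point holds as a gap between the stated abscopal aim and the response rules: nothing in Sections 6.3, 7.3.1 or 7.5.2.1.1 expressly excludes the irradiated lesion from the target lesions or the CR/PR call, and the basis of the 5% null is not stated. It should be corrected, because the count feeds both Simon decisions and the correction is cheap.

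The size is unknown and may be near zero, since the documents give neither an in-field response rate nor lesion shares. The illustrated rise from 0.042 to between 0.072 and 0.157 rests wholly on the assumed 1 to 3 points. A reader might take it to mean that the type I error is wrongly stated or is known to be inflated. The documents do not support that: the stated figures reproduce, and no in-field rate is given from which inflation could be derived. In-field shrinkage alone makes a PR only when the lesion is a large share of the sum and disease elsewhere is controlled. Confidence is medium, mainly because the intended estimand is open.

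**What to change.** In Sections 6.3 and 7.5.2.1.1, state for Cohort B that:

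- the lesion to be irradiated is identified before baseline measurement and is not selected as a target lesion;
- the primary ORR, and the count used at both Simon decisions, is based on non-irradiated lesions;
- ORR including the irradiated lesion is reported as supportive;
- the irradiated lesion enters the CR call in a specified way;
- analysis PD and PFS (Sections 7.3.2 and 7.5.3.1) stay on the PD definition the protocol already uses, with no change to any treatment-discontinuation rule.

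If the sponsor intends the combination ORR as primary, Section 7.5.2.1.1 should say so, Section 7.1.2 should put the 5% null on the same basis, and ORR in non-irradiated lesions should be reported beside it so that the abscopal aim can still be answered.

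**Cost.** This is a wording change with no new visits or scans, since criterion 9 already secures measurable disease outside the field. The downsides are fewer target lesions in some patients, a possibly lower reported ORR, and re-scoring of any scans already read; the documents do not show how many.
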